7.5.2 Overall Survival

One of the secondary objective of this study is to estimate the overall survival (OS) in all treated subjects. The median OS and 2-sided 95% confidence interval will be calculated via Kaplan-Meier (KM) estimation procedure. The survival function will be estimated using the KM product limit method and will be displayed graphically. Estimates for 3-year, 4-year, and 5-year OS rates will be presented along with their associated 95% CIs. These estimates will be come from the

KM curve and their standard errors (SEs), for use in constructing CIs, will be computed using Greenwood's formula¹⁷ and on log-log transformation applied on the survivor function.

Analyses of OS will also be conducted based on all treated population, and also by subgroups based on lines of prior therapy (2L/3L groups), or by age group (<65 years, \geq 65 years), and (<75 years, \geq 75 years). Subgroup analysis by ECOG PS (0-1,2), by response to most recent line of therapy (relapsed and refractory, relapsed, refractory, intolerant) and by ISS stage (I,II,III) if albumin and beta 2 microglobulin data are available will be conducted as well. OS is also evaluated based on 3 levels of response (VGPR or better, PR, SD or MR). OS will be estimated using the Kaplan-Meier (KM) product limit method and presented using a KM curve.

Currentness of OS data will be summarized in months, by computing the time from "last known alive" date to data cut-off date. Subjects who have a death event will be considered as current for this analysis.

A by-subject listing will be presented including OS duration, whether the subject was censored, and if censored, the reason, for all enrolled subjects.

7.5.3 Objective Response

The other secondary objective of this study is to estimate the Objective Response Rate (ORR). The number and percentage of subjects in each category of best overall response (stringent CR [sCR], complete response [CR], very good partial response [VGPR], partial response [PR], minor (minimal response) [MR], stable disease/no change [SD], progressive disease [PD], or unable to determine [UD]) will be presented. An estimate of the objective response rate and an associated exact two-sided 95% CIs (Clopper and Pearson¹⁸) will be presented. Also, the number and percentage of subjects in each category of best overall response according to the investigator tumor assessment will be presented.

Analyses of ORR will be conducted based on the all treated analysis population, and also by subgroups based on lines of prior therapy (2L, 3L), or by age group (<65 years, \geq 65 years), and (<75 years, \geq 75 years). Subgroup analysis by ECOG PS (0-1,2), by response to most recent line of therapy (relapsed and refractory, relapsed, refractory, intolerant) and by ISS stage (I,II,III) if albumin and beta 2 microglobulin data are available will be conducted as well.

7.6 Safety

7.6.1 Adverse Events

AEs will be categorized using the most recent version of the MedDRA, by system organ class (SOC) and preferred term. The severity of AEs will be graded using the NCI CTCAE (v 3.0).

On-study AEs are defined as non-serious and serious AEs with an onset date on or after the first dose until 60 days after the last dose. See Section 8.4, Imputing AE Onset Dates, for a discussion of imputation rules for incomplete or missing AE onset dates. If the relationship to study drug is missing, then the AE will be assumed to be related to study drug.

Unless specified otherwise, AEs will be counted only once within each SOC and preferred term, according to their worst CTC grade.

Tables will be sorted by SOC and preferred term, with SOCs ordered by decreasing frequency overall and then alphabetically. Preferred terms will be sorted within SOCs by descending frequency overall and then alphabetically.

Frequency table of the worst grade of on-study AE will be presented. The table will be with AEs broken out by individual grade, 1, 2, 3, 4 or 5 together with an Any Grade category. There will also be a table in which grades are grouped as follows "Any, Grade 3-4 and Grade 5". This last summary will be repeated for on-study drug-related AEs.

A by-subject listing all AEs will be presented for all treated subjects.

In addition the following will be presented:

• Exposure-adjusted AE incidence rates (including multiple occurrences of unique events) will be calculated for each SOC and preferred term.

Exposure-adjusted incidence rate per 100 person-years will be used and will be calculated as:

 $100 \times \frac{\text{Total number of unique AEs}}{\left(\frac{\text{subject date of last dose of study drug} - \\ \frac{\text{subject date of first dose of study drug} + 60 + 1}{365.25}\right)}$

and will be displayed along with a count of events

AEs can be counted multiple times within each SOC and preferred term in this summary table.

A by-subject listing of unique AEs will be provided for all treated subjects.

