6.1.1 Serious Adverse Event Collection and Reporting

Sections 5.6.1 and 5.6.2 in the Investigator Brochure (IB) represent the Reference Safety Information to determine expectedness of serious adverse events for expedited reporting. Following the subject's written consent to participate in the study, all SAEs, whether related or not related to study drug, must be collected, including those thought to be associated with protocol-specified procedures. All SAEs must be collected that occur during the screening period and within

100 days of discontinuation of dosing. If applicable, SAEs must be collected that relate to any later protocol-specified procedure (eg, a follow-up skin biopsy).

The Investigator must report any SAE that occurs after these time periods and that is believed to be related to study drug or protocol-specified procedure.

An SAE report must be completed for any event where doubt exists regarding its seriousness.

If the investigator believes that an SAE is not related to study drug, but is potentially related to the conditions of the study (such as withdrawal of previous therapy or a complication of a study procedure), the relationship must be specified in the narrative section of the SAE Report Form.

SAEs, whether related or not related to study drug, and pregnancies must be reported to BMS (or designee) within 24 hours of awareness of the event. SAEs must be recorded on the SAE Report Form; pregnancies on a Pregnancy Surveillance Form (electronic or paper forms). The preferred method for SAE data reporting collection is through the eCRF. The paper SAE/pregnancy surveillance forms are only intended as a back-up option when the eCRF system is not functioning. In this case, the paper forms are to be transmitted via email or confirmed facsimile (fax) transmission to:

SAE Email Address: Refer to Contact Information list.

SAE Facsimile Number: Refer to Contact Information list.

For studies capturing SAEs through electronic data capture (EDC), electronic submission is the required method for reporting. In the event the electronic system is unavailable for transmission, paper forms must be used and submitted immediately. When paper forms are used, the original paper forms are to remain on site.

SAE Telephone Contact (required for SAE and pregnancy reporting): Refer to Contact Information list.

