6.2.1 Nonserious Adverse Event Collection and Reporting

The collection of nonserious AE information should begin at initiation of study drug until 60 days from the last dose of study drug for patients in the EPd cohort and until 100 days from the last dose of study drug for the EN cohort. Subjects in the EN cohort who cross-over to the EPd cohort but discontinue treatment within 2 cycles of EPd treatment will still need to undergo 100 day follow-

up visit from last dose of the nivolumab to evaluate safety events related to study treatment. Nonserious AE information should also be collected from the start of a placebo lead-in period or other observational period intended to establish a baseline status for the subjects.

Nonserious AEs should be followed to resolution or stabilization, or reported as SAEs if they become serious (see Section 6.1.1). Follow-up is also required for nonserious AEs that cause interruption or discontinuation of study drug and for those present at the end of study treatment as appropriate. All identified nonserious AEs must be recorded and described on the nonserious AE page of the CRF/eCRF (paper or electronic).

Completion of supplemental CRF/eCRFs may be requested for AEs and/or laboratory abnormalities that are reported/identified during the course of the study.

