8.4.3 Safety Analyses

Safety assessments will be performed prior, during and between dosing, and up to 100 days after the last treatment for the EN cohort and 60 days after the last dose in the EPd cohort and for subjects in the EN cohort who cross-over to the EPd cohort but discontinue treatment within 2 cycles of EPd treatment safety assessments will be performed up to 100 days after the last dose of nivolumab. The frequency, severity, relationship to combination of drug treatment, seriousness, and outcomes of adverse events (AEs) will be reported for the full safety analysis set. AE severity will be graded according to the NCI Common Terminology Criteria for Adverse Events 3.0. Results of targeted physical examinations prior to each dosing cycle will be presented.

Summary statistics on vital signs at screening, pre-infusion, 30 minutes after the start of infusion, at end of infusion and 30 minutes after the completion of infusion will be reported for each dosing cycle. Concomitant medications, SAEs, laboratory parameters, and performance status prior to dosing will be presented. The safety analysis set will be used for reporting safety /adverse events.

Revised Protocol No.: 03 Date: 08-Mar-2018

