4.6 Safety and Tolerability

Safety and tolerability endpoints consist of all deaths, AEs, drug-related AEs, AEs leading to treatment discontinuation, SAEs, and drug-related SAEs and specific laboratory abnormalitites (worst grade) collected during the treatment and up to 60 days after discontinuation of study drug will be tabulated using worst grade per NCI CTCAE v3.0 criteria by system organ class and MedDRA preferred term.

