6 STUDY PERIODS, TREATMENT REGIMENS AND POPULATIONS FOR ANALYSES

6.1 Study Periods

There are three periods in this study: screening, on-treatment and post-treatment follow-up.

Screening: Most screening procedures must be done no more than 14 days prior to first dose of treatment. Some exceptions include Serum β 2-microglobulin, Pregnancy Test, Myeloma Urine and Serum Lab tests, Bone Marrow Aspiration/Biopsy, Skeletal Imaging, CT/MRI assessment for extramedullary soft tissue plasmacytoma, which can be done up to 60 days prior to first dose of study drug. See Section 5 of the Protocol for full details of study procedures and timings. For

analyses purposes data collected on or after information consent date and prior to first dose will fall into the screening/baseline period.

Baseline: Baseline evaluations will be those performed within 60 days prior to first dosing date. When an assessment is repeated multiple times within the screening period, the baseline evaluation will be the one closest to the first dosing date.

All laboratory tests and procedures done on the first date of dosing will be assumed to have occurred prior to dosing and therefore baseline evaluation for those parameters will be those prior or on the first dosing date.

On-Treatment Period: In the post baseline period, every 28 days is defined as a cycle. AEs will be defined as AEs with an onset date-time on or after the date-time of the first dose of study treatment (or with an onset date on or after the day of first dose of study treatment if time is not collected or is missing) and within 60 days of the last dose of study treatment. Subjects should have myeloma urine and serum laboratory assessments, and the tumor response assessments per IMWG uniform criteria will be every 4 weeks from date of first dose of study drug on Cycle 1 Day 1 until progression or discontinuation. Study treatment ends when the subject progresses, experiences unacceptable toxicity, or withdraws consent.

Follow-up Period: Subjects who are discontinued from further study treatment for reasons other than progression will be followed every 4 weeks for disease progression. Following disease progression, subjects will be followed at least annually for survival until the subject dies or the study ends.

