7.6.2 Serious Adverse Events and Adverse Event Leading to Discontinuation

Summaries of worst grade of on-study SAE, both by individual grade (1, 2, 3, 4, or 5, together with an Any Grade category) and by grade grouped as "Any, Grade 3-4 and Grade 5" will also be presented. This last summary will be repeated for:

- On-study drug-related SAEs
- On-study AEs leading to discontinuation.
- On-study Drug related AEs leading to discontinuation

By-subject listings of SAEs and AEs leading to study drug discontinuation will be produced for all treated subjects.

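### The SAP closes the on-study AE and SAE window at 60 days in both cohorts, but the protocol follows EN to 100 days, so EN events starting on days 61-100 enter no on-study table

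*SAP*

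**What the plan says.** **SAP.** One 60-day limit is used throughout.
- Section 4.6 describes the safety endpoints as those "collected during the treatment and up to 60 days after discontinuation of study drug".
- Section 6.1 defines AEs as those starting from first dose "and within 60 days of the last dose of study treatment".
- Section 7.6.1 defines on-study AEs as "non-serious and serious AEs with an onset date on or after the first dose until 60 days after the last dose". Its worst-grade and drug-related tables use that definition.
- Section 7.6.2 does the same for serious events ("Summaries of worst grade of on-study SAE") and for events leading to discontinuation.
- The exposure-adjusted rate in 7.6.1 divides "Total number of unique AEs" by time from first to last dose plus a fixed 60 + 1 days.
- Section 7.1 has the cohorts analysed separately, but no section gives EN its own window.

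**Protocol, Revised 03.** EN has a 100-day period.
- Section 6.2.1 collects non-serious AEs for 60 days in EPd and "until 100 days from the last dose of study drug for the EN cohort".
- Section 6.1.1 collects all SAEs within "100 days of discontinuation of dosing", without distinguishing cohorts.
- Section 8.4.3 has safety assessments "up to 100 days after the last treatment for the EN cohort and 60 days after the last dose in the EPd cohort".
- Table 5.1-6 places the EN post-treatment AE and SAE assessments at Days 30 and 100.

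**The concern.** Section 8.4.3 of the protocol is its own safety-analysis section, so the 100 days for EN is more than a collection rule. The SAP's 60 days fits the EPd schedule (visits at Days 30 and 60, Table 5.1-3) and appears to have been carried over to EN.

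At stake is whether the report's EN AE and SAE frequencies cover the period the protocol set for them. Protocol 8.4.3 promises frequency and severity, and a by-subject listing does not supply a rate. EN is a combination for which Protocol 1.5 acknowledges that unforeseen events are possible, so a truncated safety table is not a trivial omission.

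**Working it through.** There is no planned figure to reproduce. The check is a comparison of windows followed by day counts.

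**1. The gap.** EN protocol window 100 days minus SAP window 60 days = 40 days, which is 40/100 = 40% of the post-dose period.

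**2. Share of EN observation time (no crossover).** Inputs: 28-day cycles and EN dosing days from Protocol Table 4.5-2 (last elotuzumab on Day 22 in Cycles 1 and 2; Day 1 only from Cycle 5). Let L be the study day of last dose. Observation runs from day 1 to day L + 100, so the share outside the SAP window is 40/(L + 100).

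| Last dose | L | L + 100 | Share |
|---|---|---|---|
| Cycle 1 Day 22 | 22 | 122 | 32.8% |
| Cycle 2 Day 22 | 28 + 22 = 50 | 150 | 26.7% |
| Cycle 5 Day 1 | 4 × 28 + 1 = 113 | 213 | 18.8% |
| Cycle 12 Day 1 | 11 × 28 + 1 = 309 | 409 | 9.8% |

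These are maxima. They assume no skipped doses and that the patient is alive and observed for the full 100 days. They are shares of days, not of events. One EN patient whose only event of a given kind starts on days 61-100 changes a table entry by 1/30 = 3.3 percentage points.

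**3. Exposure-adjusted rate.** The SAP denominator is (L − 1) + 60 + 1 = L + 60 days. A 100-day window makes it L + 100 before any truncation. The numerator and this term therefore have to move together.

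**4. Crossover patients.** Protocol 6.2.1 and 8.4.3 follow those who stop EPd within 2 cycles to 100 days after last nivolumab. I assume the SAP's last dose is then the last EPd dose and that EPd starts on Day 1 of the next cycle. If EPd starts g days after last nivolumab and its last dose is d days after that, the SAP window closes g + d + 60 days after last nivolumab. The shortfall is max(0, 100 − that). The permitted nivolumab delays are from Protocol 4.5.4. A full EPd cycle ends with dexamethasone on Day 22, so d = 21.

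| Case | g + d + 60 | Shortfall |
|---|---|---|
| After Cycle 2, EPd Day 1 only | 14 + 0 + 60 = 74 | 26 days |
| After Cycle 5, EPd Day 1 only | 28 + 0 + 60 = 88 | 12 days |
| After Cycle 2, one full EPd cycle | 14 + 21 + 60 = 95 | 5 days |
| After Cycle 5, one full EPd cycle | 28 + 21 + 60 = 109 | 0 days |
| After Cycle 2, last nivolumab 3 days late, EPd Day 1 only | 11 + 0 + 60 = 71 | 29 days |
| After Cycle 5, last nivolumab 7 days late, EPd Day 1 only | 21 + 0 + 60 = 81 | 19 days |

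**5. EPd.** Non-serious AEs agree at 60 days. For SAEs the protocol disagrees with itself: 60 days in 8.4.3, but 100 days in 6.1.1 and in the SAE note of Table 5.1-3.

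**The case against.** The best defence is that little is lost. SAP 7.6.1 plans a by-subject listing of all AEs, and 7.6.4 summarises all deaths as well as those within 60 days. SAP 8.4 defers to sponsor safety conventions and section 9 to a Data Presentation Plan, neither of which is available here. The SAP history entry for version 1.2 warns that the SAP might not match the protocol while Amendment 03 was being finalised.

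The mitigation stands in part. Late deaths are kept. Late AEs should be listed, although the AE definition in 6.1 makes even that less than certain. The rest does not close the gap: 7.6.1 states 60 days outright. Later SAP versions also took in the Amendment 03 draft, the EN sample size and nivolumab dose intensity without changing the window.

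Three stronger readings are tempting and are not supported:
- **The on-study tables would contradict the stopping rule in Protocol 4.5.10.** That rule has its own window, 100 days from last nivolumab. It counts Grade 3 or higher immune-related events, and Grade 5 events not due to progression, in the first half of treated patients. The SAP plans no such table, so there is nothing to contradict.
- **The exposure-adjusted rate is inflated by late events over a 60-day denominator.** Its numerator, "Total number of unique AEs", carries no window of its own, but SAP 6.1 already limits AEs to 60 days. On the natural reading numerator and denominator agree with each other; they do not agree with the EN protocol period.
- **The laboratory window in SAP 7.6.5 must be extended too.** Table 5.1-6 schedules no blood count or chemistry at Days 30 or 100, so there is little basis for this.

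**Conclusion.** The mismatch is real and sits in current text. As written, the SAP leaves EN AEs and SAEs with onset on days 61-100 out of every on-study frequency table. An event that starts by day 60 but is first reported at the Day 100 visit is still counted.

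For EN patients who do not cross over, the size is 40 of 100 post-dose days, under the assumptions given with the table of shares. For crossover patients who stop EPd early, the shortfall is 0 to 26 days if dosed on schedule and up to 29 days with permitted nivolumab delays. The number of events affected cannot be derived from the documents. No efficacy analysis is touched, and the stopping rule operates unchanged. The EPd SAE period is a point for the protocol to clarify, not an established SAP error. This should be fixed before the EN safety tables are produced; it does not threaten the trial's conclusions.

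**What to change.** - In SAP 4.6, 6.1 and 7.6.1-7.6.2, set the EN on-study AE and SAE window to 100 days after last dose. Keep 60 days for EPd non-serious AEs.
- In the exposure-adjusted rate, apply the same cohort window to numerator and denominator. End each patient's time at the earliest of last dose plus window, death and data cut-off, in place of the fixed 60 + 1 days.
- For crossover patients who stop EPd within 2 cycles, carry the window to at least 100 days after last nivolumab, in line with Protocol 6.2.1.
- Reconcile Protocol 8.4.3 with 6.1.1 and Table 5.1-3 on EPd SAEs, then state in the SAP which window the EPd SAE tables use.
- Footnote the different cohort windows, and flag EN events that start after subsequent anti-myeloma therapy.

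The cost is SAP wording and a programming parameter; the EN AE and SAE data are already collected. The downside is that EN frequencies may rise slightly and may include events that follow later therapy, which the flag makes visible.
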